#### **1.2.4 Description of the drugs and devices to be studied**

Xylocaine (lidocaine HCl) is a common local anesthetic that works by stabilizing the neuronal membrane by inhibiting the ionic fluxes required for the initiation and conduction of impulses. Local anesthetics of the amide type are thought to act within the sodium channels of the nerve membrane. According to the packaging insert, anesthesia is achieved within 5 minutes, depending on the area of application, and duration of anesthesia is approximately 20-30 minutes.

For paracervical block the drug label recommends a maximum dose of 200 mg (100 mg per side) in a 90 minute periodix. Given risk of rapid systemic absorption and possible maternal seizure and cardiovascular collapse, the maximum dose should not be exceeded. The label also recommends slow injection and a 5-minute interval between each side.

Contraindications to lidocaine include the following:

- Hypersensitivity to lidocaine or any component of the formulation
- Hypersensitivity to another local anesthetic of the amide type
- Adam-Stokes syndrome
- Wolff-Parkinson-White syndrome
- Severe degrees of SA, AV, or intraventricular heart block (except in patients with a functioning artificial pacemaker)
- Premixed injection may contain corn-derived dextrose and its use is contraindicated in patients with allergy to corn or corn-related products

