#### **1.2.5 Admission procedure**

Eligible women will be screened and identified in two ways. The first will be via prospective chart review done by Stanford clinical research personnel. The second will be providers and clinic staff informing clinical research personnel of potential participants.

If potential participants meet inclusion criteria and permission has been granted by their provider, they will be approached by a clinical research coordinator who will review the study protocol and obtain informed consent. After obtaining informed consent, participants will be randomized to a study arm via computer-generated block randomization using REDCap

software. The provider and staff will be aware of arm allocation, but participants will remain blinded.

There will be two study arms:

Experimental:

- Syringe loaded with 12 mL of 1% lidocaine (120 mg); 22-gauge spinal needle
- 2 mL injected at the tenaculum site, either 6 or 12 o'clock superficially into the cervix
- The tenaculum is immediately placed at the previously injected site
- The remaining 10 mL are slowly injected into the cervicovaginal junction in two equal aliquots at 4 and 8 o'clock; the injection is continuous from superficial to deep (3 cm) to superficial (injecting with insertion and withdrawal)
- No wait time between injection and dilator insertion

Control:

- Syringe loaded with 20 mL of 1% lidocaine (120 mg); 22-gauge spinal needle
- 2 mL injected at the tenaculum site, either 6 or 12 o'clock superficially into the cervix
- The tenaculum is immediately placed at the previously injected site
- The remaining 18 mL are slowly injected into the cervicovaginal junction in two equal aliquots at 4 and 8 o'clock; the injection is continuous from superficial to deep (3 cm) to superficial (injecting with insertion and withdrawal)
- No wait time between injection and dilator insertion

Prior to the procedure, clinical research coordinators will obtain the following baseline information using REDCap:

- Demographics
  - Location of procedure
  - MRN
  - Date enrolled
  - First name
  - Last name
  - Date of birth
  - Age
  - Phone number
  - Race
  - Ethnicity
- Medical History (Physical Exam and Ob/Gyn History)
  - Height
  - Weight
  - BMI
  - First day of last menstrual period
  - Gestational age defined by U/S
  - Medication allergies
  - Current medications
  - Number of previous pregnancies
    - Number of previous vaginal deliveries

- Number of previous cesarean sections

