- Number of previous abortions
- Number of previous abortions after 16 weeks gestation
- Number of miscarriages
- Recent deliveries
- Medical problems
- Previous surgeries
  - Previous cervical surgeries
  - Other previous surgeries

The participant will then be prepped for the procedure. At that point, the clinical research coordinator will accompany participants throughout the duration of their procedure and obtain the following information:

- Procedure Data
  - Provider type (i.e. resident, fellow, attending)
  - Provider reported ease of procedure
  - Initial cervical dilation
  - Uterine position
  - Number of osmotic dilators placed
  - Total procedure time, as defined by speculum time
  - Digoxin given
  - Complications
    - Inability to dilate cervix
    - Seizure
    - Cardiac arrest
    - Structural trauma (uterine perforation, cervical laceration, etc.)
    - Hemorrhage (EBL estimation)
  - Administration of Mifepristone for cervical preparation
- Procedure VAS Data
  - Anticipated Pain: 30 minutes prior to procedure
  - Baseline Pain: Immediately prior to procedure
  - Block injection Pain: Immediately following injection, but prior to dilator insertion
  - Dilator Insertion Pain: Immediately following dilator insertion
  - Post-procedure Pain: 10-15 minutes following procedure
  - Overall Pain: Assessed after procedure (prior to discharge)
- Symptom Data
  - Following block injection, any experience of:
    - Metallic taste in mouth
    - Ringing in ears
    - Lightheadedness
  - Any other systemic symptoms experienced, including vasovagal reaction
- Acceptability Data
  - Global satisfaction with procedure
- Recognition of group allocation

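### The listed procedure data have no field for lidocaine volume delivered or added anesthetic, and no analysis population is defined, so most departures that dilute the 12 versus 20 mL contrast could not be identified

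*Combined protocol and SAP*

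**What the plan says.** All references are to the combined protocol and SAP.

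- **Arms (1.2.5).** The experimental instruction begins "Syringe loaded with 12 mL of 1% lidocaine (120 mg); 22-gauge spinal needle" and the control instruction "Syringe loaded with 20 mL of 1% lidocaine (120 mg); 22-gauge spinal needle". Each arm uses 2 mL at the tenaculum site. The experimental arm then receives 10 mL at 4 and 8 o'clock; for control, "The remaining 18 mL are slowly injected into the cervicovaginal junction in two equal aliquots". Both arms carry the rule "No wait time between injection and dilator insertion".
- **Blinding (1.2.5).** "The provider and staff will be aware of arm allocation, but participants will remain blinded".
- **Data collected (1.2.5).** During the procedure, "the clinical research coordinator will accompany participants throughout the duration of their procedure and obtain the following information". The items are provider type, ease, initial dilation, uterine position, dilator count, speculum time, digoxin, complications, mifepristone, six VAS scores, symptoms, satisfaction, and whether the woman recognized her allocation. The only duration is "Total procedure time, as defined by speculum time".
- **Discontinuation (1.2.7).** A woman who needs more cervical anesthesia, or an intervention for a complication, leaves the study.
- **Data management (1.2.9)** makes only general statements about coding, monitoring and verification.
- **Analysis (1.2.10)** names tests and a regression. It defines neither an as-randomized nor a per-protocol population and does not say how discontinued women are handled.

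**The concern.** The trial asks whether 12 mL controls dilator-insertion pain no worse than 20 mL by more than 15 mm. That question is answered only if the two volumes were actually given. In a superiority trial, blurred treatment contrast usually counts against the new treatment. Here it counts in its favor: if 12 mL is truly worse, control blocks delivered at less than 20 mL shrink the observed difference.

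The documents make such departures plausible. Providers are unblinded. Section 1.1.1 says that symptoms are more likely with 20 mL, and it equates 20 mL at 1% with the 200 mg label maximum. A provider could therefore have a reason to stop a control block early. Both syringes are also labelled 120 mg in 1.2.5, which conflicts with 1.1.1. Those passages must be reconciled, and meanwhile a syringe prepared from the milligram figure rather than the milliliter figure would not be visible in the listed data. Providers range from residents to attendings at two sites, so technique may vary.

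Volumes that are not written down at the time may not be recoverable, so this should be settled before enrollment.

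**Working it through.** **1. Fields needed against fields listed (1.2.5)**

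| Needed to verify the contrast | Listed? |
|---|---|
| mL delivered, total | No |
| mL at tenaculum site, 4 and 8 o'clock | No |
| Additional local anesthetic (type, mL, time) | No field; 1.2.7 discontinues women who require it |
| Injection-to-insertion interval | No; only speculum time |

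**2. Planned contrast.** Block volume: 18 − 10 = 8 mL. Total volume: 20 − 12 = 8 mL.

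**3. The plan's own figure (1.2.11).** Inputs: SD 28, margin 15 mm, power 80%, N = 88. Assumed because not stated: 1:1 allocation and true difference 0. The formula is n per arm = 2 × [28 × (z₁₋α + 0.842) / 15]².

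- One-sided 0.025, the stated interval: 2 × [28 × (1.960 + 0.842) / 15]² = 54.7, so 55 per arm and 110 in total.
- One-sided 0.05: 2 × [28 × (1.645 + 0.842) / 15]² = 43.1, so 44 per arm and 88 in total.

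The 88 therefore reproduces only at one-sided 0.05. That is a separate point. It matters here only because the illustration has to be shown at both levels.

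**4. Effect of lost contrast.** Assume that the true difference under full delivery equals the margin, 15 mm, and that the effect is linear in volume. If a fraction f of the 8 mL contrast is lost, the expected difference is 15(1 − f).

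- SE = 28 × √(2/44) = 5.97 mm.
- At one-sided 0.025, non-inferiority is declared if the estimate is below 15 − 1.960 × 5.97 = 3.30 mm.
- P(false non-inferiority) = Φ(15f/5.97 − z₁₋α).

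| Mean loss | f | Expected difference | 15f/SE | Risk, one-sided 0.025 | Risk, one-sided 0.05 |
|---|---|---|---|---|---|
| 0 mL | 0 | 15.0 mm | 0 | 2.5% | 5.0% |
| 0.4 mL | 5% | 14.25 mm | 0.126 | Φ(−1.834) = 3.3% | 6.4% |
| 1 mL | 12.5% | 13.1 mm | 0.314 | Φ(−1.646) = 5.0% | 9.2% |
| 2 mL | 25% | 11.25 mm | 0.628 | Φ(−1.332) = 9.1% | 15.5% |

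A mean loss of 0.4 mL would arise, for example, if 20% of control blocks were 2 mL short (0.20 × 2 = 0.4). A mean loss of 2 mL requires every control block to be 2 mL short, or a smaller share to be further short.

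**5. Direction.** A shortfall confined to the control arm, or extra volume in the 12 mL arm, narrows the contrast. A shortfall confined to the 12 mL arm widens it and works against non-inferiority. The listed data could not tell these apart.

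**The case against.** There are five fair counter-arguments.

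- **Section 1.2.7 already deals with top-ups.** A reader might infer that a supplemented 12 mL block would simply be analyzed as 12 mL with no trace. The documents do not support that: women requiring more cervical anesthesia are to be identified and discontinued. This stands, within limits. The rule does not cover under-delivery or a wrong volume drawn up, 1.2.5 has no field for the added drug, and 1.2.10 does not say whether these women are analyzed.
- **The syringe is loaded to the assigned volume.** Over-delivery in the 12 mL arm would need more to be drawn up. This stands, and leaves under-delivery in the control arm as the main route.
- **Timing.** Section 1.2.4 says "anesthesia is achieved within 5 minutes, depending on the area of application", and a reader might infer that unrecorded waiting pulls the arms together. The no-wait rule is common to both arms, and the rationale in 1.1.1 cites two studies that found no significant difference in dilation pain between waiting and not waiting. Mistiming does not reduce the volume contrast and could move the result either way. Timing is not part of the case.
- **Larger figures.** Supposing that 10% to 30% of one arm effectively received the other arm's full volume gives a false non-inferiority risk of 4.4% to 11.4% at one-sided 0.025. The arithmetic is right, but complete crossover is not what a block cut short looks like.
- **A protocol list is not a case report form.** The form is not in the documents, so they show only that the fields are not listed, not that nothing will be recorded. This stands.

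**Conclusion.** The point holds in limited form, as a change the plan should make. The listed data omit delivered volume and additional anesthetic, and 1.2.10 defines no analysis population. Apart from the discontinuation rule in 1.2.7, departures that dilute the 12 versus 20 mL contrast cannot be identified from the listed data.

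The illustrated cost is modest for small losses and material for larger ones: from 2.5% to about 3.3%, 5.0% or 9.1% for mean losses of 0.4, 1 or 2 mL. It rests on a true difference exactly at the margin, linearity in volume, SD 28, 44 per arm and one-sided 0.025. The documents give no departure rate, so they do not show that such losses will occur. If the two volumes are truly equivalent, dilution introduces no bias.

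A reader might also infer that toxicity symptoms become uninterpretable. They do not: 1.2.10 compares them between randomized groups, which is the valid main comparison. What is lost is only a secondary, non-randomized look at symptoms by dose received.

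**What to change.** 1. **Procedure Data in 1.2.5.** Add REDCap fields for mL of 1% lidocaine delivered at the tenaculum site, at 4 o'clock and at 8 o'clock, and for the type, mL and time of any additional local anesthetic.
2. **Primary analysis in 1.2.10.** State that the as-randomized analysis of dilator-insertion VAS includes every randomized woman with a score, including those discontinued under 1.2.7. State also that the score is still sought from them.
3. **Supportive analysis in 1.2.10.** Beside it, report an analysis restricted to women who received the assigned block volume. Classify by the block itself, and do not exclude a woman because the block failed and more anesthetic was needed. If failures are commoner after 12 mL, excluding them would remove poor outcomes mainly from that arm and favor non-inferiority. Even so, this analysis is open to selection and should not replace the as-randomized result.
4. **Tables.** Report delivered volume and additional anesthetic by arm. Injection-to-insertion time is optional and descriptive.

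The cost is a few fields completed by a coordinator already in the room, one supportive analysis, and slightly more recording during a short procedure. The sample size does not change on this account.

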## **1.2.6 Follow-up procedure**

No follow-up required.

## **1.2.7 Criteria for discontinuation**

Participants requiring additional cervical anesthesia or intervention due to complication during the dilation procedure will be discontinued from the study.

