### **1.1.2 Objectives and hypothesis**

We hypothesize that a 2-site, 12 mL 1% plain lidocaine injection paracervical block (PCB) technique (2 mL for tenaculum placement, 10 mL for paracervical block) will provide non-inferior pain control compared to a previously established 2-site, 20 mL 1% lidocaine injection PCB (2 mL for tenaculum placement, 18 mL for paracervical block) when administered for dilation pain control during cervical preparation.

Our primary objective is to determine pain perceived at time of dilator insertion measured by Visual Analogue Scale (VAS; Dilator Insertion: Immediately following dilator insertion) (0-100mm).

Secondary objectives include assessing:

- Pain perceived at additional time points before, during, and after the procedure (all measured by VAS (0-100mm; 0 being no pain and 100 being worst pain imaginable):
  - o Anticipated Pain: 30 minutes prior to procedure

- Baseline Pain: Immediately prior to procedure
- Block injection Pain: Immediately following injection, but prior to dilator insertion
- Post-procedure Pain: 10-15 minutes following procedure
- Overall Pain: Assessed after procedure (prior to discharge)
- Total procedure time, as defined by speculum time
- Incidence of complications
  - Inability to dilate cervix
  - Seizure
  - Cardiac arrest
  - Structural trauma (uterine perforation, cervical laceration, etc.)
  - Hemorrhage (EBL estimation)
- Symptom Data
  - Following block injection, any experience of:
    - Metallic taste in mouth
    - Ringing in ears
    - Lightheadedness
- Any other systemic symptoms experienced, including vasovagal reaction
- Provider reported ease of insertion
- Global satisfaction (acceptability) of procedure reported by participant (VAS, 0-100mm; 0 being unsatisfied and 100 being fully satisfied)

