## **1.2.10 Data analysis**

Perioperative characteristics will be examined among the groups using chi square test and fisher's exact test, where appropriate; mean and median VAS pain scores will be analyzed with Student's *t*-tests and non-parametric tests, respectively; mean and median overall satisfaction with pain control and provider reported ease of procedure via VAS scores will be compared using Student's *t*-tests and non-parametric tests, respectively; linear regression will be completed in multivariable analysis to identify predictors of pain. Complications and patient symptoms associated with lidocaine toxicitiy will be examined between the groups using chi square test and fisher's exact test, where appropriate.

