## **1.2.11 Number of subjects and statistical power**

88 participants are required to be 80% sure that the lower limit of a one-sided 97.5% confidence interval (or equivalently a 95% two-sided confidence interval) will be less than the non-inferiority limit of 15mm. Accounting for participant drop-out, we will recruit 96 women to participate in this study (significance level, alpha of 5%; power of 80%; standard deviation of 28; non-inferiority limit of 15).

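### Women who need additional cervical anesthesia are discontinued, and the plan does not say whether they stay in the primary analysis or which score they get; dropping them can, under stated conditions, favour non-inferiority

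*Combined protocol and SAP*

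**What the plan says.** Section 1.2.7 (Criteria for discontinuation) is one sentence: "Participants requiring additional cervical anesthesia or intervention due to complication during the dilation procedure will be discontinued from the study".

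Section 1.2.5 lists the primary measurement as "Dilator Insertion Pain: Immediately following dilator insertion". It also states that the provider and staff "will be aware of arm allocation, but participants will remain blinded".

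Section 1.2.10 (Data analysis) states that "mean and median VAS pain scores will be analyzed with" t-tests and non-parametric tests. It defines no analysis set, gives no rule for a score taken after additional anesthesia, and names no missing-data method. The same section says "Complications and patient symptoms associated with lidocaine toxicitiy will be examined between the groups", and section 1.1.2 lists "Incidence of complications" among the secondary objectives.

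Section 1.2.11 says only "Accounting for participant drop-out, we will recruit 96 women to participate in this study". It gives neither a rate nor reasons for drop-out.

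The copy reviewed has no section 1.3, so the statement that no rule exists covers the rest of the document.

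**The concern.** The trial asks whether a smaller block controls pain during dilator insertion well enough. A woman who needs more cervical anesthesia during that procedure is plausibly one whose block did not work. Taking her out of the comparison would remove an informative result, through an event after randomization, in the hands of a provider who knows the arm.

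The two readings of *discontinued* raise different problems:

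- **She is excluded from the primary comparison.** The remaining scores in each arm are then selected on something related to the outcome.
- **She is kept.** Her score is due after insertion and so may be taken after the extra anesthetic. No rule says whether that score counts. A woman whose cervix cannot be dilated may have no insertion score at all.

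In a superiority trial, shrinking a true difference works against the claim. Here the claim is that the difference is below 15 mm, so shrinkage works in its favour.

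**Working it through.** **Inputs from the plan.** Section 1.2.11 gives "significance level, alpha of 5%; power of 80%; standard deviation of 28; non-inferiority limit of 15". It recruits 96 women, so 48 per arm. The allocation ratio is not stated; 1:1 is assumed.

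**Inputs assumed, because the documents give none.** Control mean 40 or 50 mm. Women scoring above 80 or 90 mm are lost with probability p = 0.25 or 0.50, the same in both arms. The true difference is set at the 15 mm margin, where every non-inferiority claim is an error.

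**Step 1: the plan's own figure.** n per arm = 2 × (z for alpha + z for power)² × 28² / 15².

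- One-sided 5%: 2 × (1.645 + 0.842)² × 784 / 225 = 43.1, so 44 per arm and 88 in total, as stated.
- One-sided 2.5%, which matches the 97.5% interval the section names: 2 × (1.960 + 0.842)² × 784 / 225 = 54.7, so 55 per arm and 110 in total.

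That mismatch is a separate matter. Because of it, both error levels are shown below. The drop-out allowance is 8/96 = 8.3%.

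**Step 2: shift in the mean.** For normal scores let z = (threshold − arm mean) / 28, with Q the upper tail area and φ the density at z. Share lost = p × Q. Fall in the arm's mean = 28 × p × φ / (1 − p × Q).

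Example: control mean 40, threshold 90, p = 0.50.

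- 12 mL arm (mean 55): z = 35/28 = 1.25, Q = 0.1056, φ = 0.1826. Share lost 5.3%; fall 28 × 0.5 × 0.1826 / 0.9472 = 2.70 mm.
- 20 mL arm (mean 40): z = 50/28 = 1.786, Q = 0.0371, φ = 0.0810. Share lost 1.9%; fall 28 × 0.5 × 0.0810 / 0.9815 = 1.16 mm.
- Expected difference: 15 − 2.70 + 1.16 = 13.46 mm.

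**Step 3: false non-inferiority.** These come from 40,000 simulated trials per scenario, with the pooled-t upper limit compared with 15 mm. With no loss the error is 2.3-2.6% and 4.8-5.1%.

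| Control mean, threshold | p | % lost, 12 mL / 20 mL | Expected difference (mm) | Error at 2.5% | Error at 5% |
|---|---|---|---|---|---|
| 40, 90 | 0.25 | 2.6 / 0.9 | 14.3 | 3.3% | 6.4% |
| 40, 90 | 0.50 | 5.3 / 1.9 | 13.5 | 4.5% | 8.4% |
| 40, 80 or 50, 90 | 0.25 | 4.6 / 1.9 | 14.1 | 3.7% | 7.0-7.1% |
| 40, 80 or 50, 90 | 0.50 | 9.3 / 3.8 | 13.0 | 5.5-5.7% | 10.0-10.3% |
| 50, 80 | 0.25 | 7.4 / 3.6 | 14.0 | 3.7% | 7.0% |
| 50, 80 | 0.50 | 14.8 / 7.1 | 12.7 | 6.0% | 10.7% |

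Two pairs share a row because only the distance from mean to threshold matters under the normal model.

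VAS scores cannot exceed 100 mm. Repeating this with scores bounded at 0-100 gives 3.0-6.3% at the 2.5% level. Over both models the difference reads about 12.4-14.4 mm.

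When the true difference lies beyond the margin, the p = 0.50 scenarios (normal scores, 2.5% level) give 0.6-0.7% rising to 1.4-2.3% at 18 mm, and 0.2-0.3% rising to 0.7-1.1% at 20 mm.

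**Step 4: other patterns of loss.** Here the loss rate is fixed by arm and has correlation 0.5 with pain (20,000 trials each, 2.5% level).

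| % lost, 12 mL / 20 mL | Difference (mm) | Error |
|---|---|---|
| 10 / 2 | 13.0 | 5.0% |
| 5 / 5 | 15.0 | 2.3% |
| 8.3 / 8.3 | 15.0 | 2.5% |
| 2 / 10 | 17.0 | 1.0% |

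Loss at the step 3 rates but unrelated to pain leaves 15.0 mm and 2.5-2.6%.

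**Step 5: women kept, but scored after rescue.** If additional anesthesia lowers the recorded score by an assumed 20 mm, error in the step 3 normal-score scenarios is 2.8-4.8%, against 3.3-6.0% if the women are dropped.

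**The case against.** The plan never says that these women leave the analysis. This is a one-visit study without follow-up, and complications are collected and compared between arms, so women with complications must be retained for at least that purpose. *Discontinued* may mean only that participation ends. This stands: exclusion is the natural reading of the sentence but not an explicit rule. It does not remove the problem, because the retained reading also lacks a score rule.

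The size has no source in the documents. Rescue rates, control mean and the link with pain are all assumed. This stands in full. On the bounded scale some of the heavier-loss scenarios also exceed the 8.3% allowance, so the assumed losses cannot all be described as within what the plan expects.

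The direction is not fixed. This stands too: equal or unrelated loss causes no shift, and heavier pain-related loss in the 20 mL arm makes non-inferiority harder to show. For women discontinued because of a complication the direction is unclear.

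A reader might infer from the open-label provider that rescue will be given differently by arm. The documents support only that the provider knows the arm. The step 3 runs use the same rule in both arms and do not model such behaviour.

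**Conclusion.** The concern holds in a conditional form. The plan states a discontinuation rule triggered by an event plausibly tied to the primary outcome, and says neither whether the affected women stay in the primary comparison nor what score they carry. If they are dropped, the 12 mL block is truly worse, and rescue follows pain, the estimated difference shrinks. Under the assumed rates a true 15 mm difference reads about 12.4-14.4 mm, and false non-inferiority goes from 2.5% to about 3-6%. That is modest.

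Two stronger readings are tempting and not supported. One is that the protocol excludes block failures from the primary analysis; it does not say so. The other is that the design is biased toward non-inferiority; that needs the conditions above, and the documents give no rates to test them.

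The point should be fixed because a scoring rule is credible only if set before data are seen. Confidence is medium: the gap is clear, its size is not.

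**What to change.** The change concerns study status and data use only; clinical care stays as it is.

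**Section 1.2.7.** State that women who receive additional cervical anesthesia, or an intervention due to a complication, remain in the study and continue to give the planned VAS, symptom and complication data where possible.

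**Section 1.2.10, before data are seen.**

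- The primary comparison analyses all randomized women in their assigned arm.
- One primary score is fixed for women given additional anesthesia, by default the observed dilator-insertion VAS.
- A rule covers women with no such score, for example when the cervix cannot be dilated.
- Need for additional anesthesia and missing primary scores are reported by arm.
- A sensitivity analysis gives rescued women an unfavourable score, for example 100 mm.

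A VAS taken just before additional anesthesia, without delaying care, is an option and not a requirement. It would be a new assessment, possibly made before all dilators are in, so not exactly the endpoint in section 1.2.5. Section 1.5 already expects difficulty in obtaining scores on time.

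**Cost.** A short amendment and a little more data collection and analysis; a coordinator already accompanies each participant. The default score can still mask part of a true difference (step 5), which the sensitivity analysis addresses. The 100 mm score should stay a sensitivity analysis. With no true difference and an assumed 10% versus 2% rescue unrelated to pain, it would cut power at the 2.5% level from 74% to 37-44%.

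### Section 1.2.7 discontinues women because of events that the safety outcomes are meant to count, and nothing says that their data still contribute

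*Combined protocol and SAP*

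**What the plan says.** Section 1.1.2 makes "Incidence of complications" a secondary objective, listing failed dilation, seizure, cardiac arrest, structural trauma and hemorrhage. Symptoms of lidocaine toxicity are a further secondary objective. Section 1.2.10 gives the comparison: "Complications and patient symptoms associated with lidocaine toxicitiy will be examined between the groups using chi square test and fisher's exact test". It names no analysis population.

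Section 1.2.7 is one sentence: "Participants requiring additional cervical anesthesia or intervention due to complication during the dilation procedure will be discontinued from the study".

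Section 1.2.5 describes data collection: "the clinical research coordinator will accompany participants throughout the duration of their procedure and obtain the following information". The list that follows includes the complications, the pain scores and a symptom checklist introduced by "Following block injection, any experience of". The last two pain scores are taken 10-15 minutes after the procedure and before discharge. Section 1.2.6 reads: "No follow-up required".

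**The concern.** The trigger for leaving the study overlaps with the outcome. A complication serious enough to need intervention is a case for the incidence count and also the reason for discontinuation. A woman given more anesthetic has a higher lidocaine exposure than her arm prescribes, and she may leave before her later symptoms are asked about.

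If the rule were applied literally, incidence would be computed mainly on women whose procedure went smoothly. Both arms would be undercounted. The comparison itself would be biased if the triggers occur at different rates by arm. That is plausible: section 1.1.1 expects toxicity symptoms to be more likely with 20 mL, and providers, who know the allocation (sections 1.2.5 and 1.2.12), may give extra anesthetic more readily in one arm.

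Fewer lidocaine symptoms is a stated reason for testing the smaller volume (section 1.1.1), and section 1.6 names it as a possible implication. These secondary outcomes would have to support that message.

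**Working it through.** **1. What is left to discontinue.** In section 1.2.5 the block is a single administration, followed without a wait by dilator insertion. The trigger in section 1.2.7 falls during dilation. The study treatment is complete by then, so leaving the study can mainly mean leaving observation or analysis.

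**2. Which safety data are exposed.**

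| Item | Exposed under a literal reading? |
|---|---|
| Complication needing intervention | Yes: it is the trigger. It may be recorded as it happens, but its place in the analysis is not stated |
| Complication needing no intervention | No |
| Symptoms noted soon after injection | Probably recorded before any trigger, but their place in the analysis is not stated |
| Symptoms emerging during or after dilation | Yes: the checklist has no stated assessment time |
| Extra anesthetic | Not a listed field in section 1.2.5, so its use by arm need not be recorded at all |

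**3. Whether another section closes the gap.** Section 1.2.5 sets the general schedule and does not mention discontinued women. Section 1.2.10 names no population. Section 1.2.6 provides no later contact at which missing data could be recovered. Section 1.2.11 raises 88 to 96 for drop-out, an allowance of 8/96 = 8.3%, without saying whether discontinued women are drop-outs.

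**4. Illustration of size.** The plan gives no figure of its own on this point. The recruitment target N = 96 comes from section 1.2.11. The true complication rate p and the share s of cases that need intervention are assumptions. If those cases are dropped:

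- expected cases = 96 × p
- counted cases = 96 × p × (1 − s)
- observed rate = p(1 − s)/(1 − ps)

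| p | Expected | Counted, s = 25% | Counted, s = 50% | Counted, s = 100% |
|---|---|---|---|---|
| 2% | 1.92 | 1.44 | 0.96 | 0 |
| 5% | 4.8 | 3.6 | 2.4 | 0 |
| 10% | 9.6 | 7.2 | 4.8 | 0 |

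For bias between arms, let p be the same in both arms, with s = 25% in one and 50% in the other:

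- p = 10%: 0.075/0.975 = 7.7% against 0.05/0.95 = 5.3%, a spurious difference of 2.4 percentage points
- p = 5%: 0.0375/0.9875 = 3.8% against 0.025/0.975 = 2.6%, a difference of 1.2 points
- p = 2%: 0.015/0.995 = 1.5% against 0.01/0.99 = 1.0%, a difference of 0.5 points

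These figures show direction and mechanism only.

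**The case against.** A reader might infer that the plan stops collecting data on these women, so that seizure and cardiac arrest must come out as zero. The documents do not support that. Section 1.2.7 says nothing about stopping data collection, deleting records or excluding anyone from analysis. Section 1.2.5 keeps the coordinator in attendance for the whole procedure with complications as named fields, and a seizure or laceration has to be seen before it can trigger discontinuation. The s = 100% column above is the extreme of an assumed range, not a prediction.

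Other limits also stand. Complications without intervention are untouched. The symptom checklist is tied to the injection, so part of it may well be complete before any trigger. A need for extra anesthetic is not in itself a toxicity event. The absence of follow-up applies to every participant and is not a consequence of discontinuation. Severe events in 96 women would be few under any rule.

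These arguments limit the likely loss but do not remove the gap. Section 1.2.5 is the general schedule, section 1.2.7 is the specific rule for women who leave, and no section says that the schedule continues for them. Even if the triggering event is recorded, nothing says that it is counted in the comparison.

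**Conclusion.** The concern holds as an unresolved conflict between section 1.2.7 and sections 1.1.2, 1.2.5 and 1.2.10. Followed literally, the discontinuation rule is an outcome-dependent exclusion. It would undercount complications that need intervention and symptoms that appear later, and could distort the comparison if the triggers differ by arm. Whether this happens depends on how sites read the rule, and its size cannot be computed from the documents. The illustrative counts rest wholly on assumed rates and on the assumption that the affected cases are dropped.

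The point is limited to the safety outcomes. The plan is equally silent on whether these women stay in the primary comparison of pain at dilator insertion, which is a separate matter. The text should be settled in advance, because data not taken at the visit cannot be recovered at a later study contact.

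**What to change.** Reconcile section 1.2.7 with sections 1.1.2, 1.2.5 and 1.2.10:

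- State in 1.2.7 that these events neither end study data collection nor remove a woman from analysis, and that the triggering event is counted as an outcome.
- Continue the complication and symptom records through the existing contacts at 10-15 minutes and before discharge.
- State in 1.2.10 that complication and symptom incidence is computed on all women who received the block, by randomized arm.
- Add extra cervical anesthetic to the data fields in 1.2.5 and report its use by arm.

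The cost is a few amended sentences, one new field and brief extra data entry for a few women at contacts that already exist. There is one trade-off: symptoms after extra anesthetic are counted in the randomized arm although they may partly reflect the added dose. Each symptom should therefore be flagged as occurring before or after it. No change to clinical management is proposed.
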